### **Secondary:**

1. Change in radiographic angular/positional alignment before and after the Lapiplasty® Procedure [Time Frame: pre-operatively, 6 weeks, 4 months, 6 months, 12 months, and 24 months, post-Lapiplasty® Procedure].
2. Evaluate clinical/radiographic healing (union vs non-union). Non-union defined as lucency at TMT joint, hardware failure and/or loss of correction (recurrence), plus clinical pain at first TMT joint at 12 months post- Lapiplasty® Procedure.
3. Clinical complications through 24-month follow-up visit due to the Lapiplasty® System Implants, the Lapiplasty® Procedure, the post-operative weight-bearing protocol or health conditions that could affect other outcome measures.
4. Time to start weight-bearing in a boot, in days.
5. Time to start weight-bearing in shoes, in days.

6. Time to return to full unrestricted activity, in days.
7. Change in pain at the base of the big toe (bunion related) assessed via a Visual Analog Scale (VAS) at 0-14 days, 14-21 days, 6 weeks, 4 months, 6 months, 12 months and 24 months post-Lapiplasty® Procedure, in comparison to baseline visit pain.
8. Change in Quality of Life, (PROMIS-29, PROMIS-25 and MOxFQ) defined as the total score measured at 6 months, 12 months and 24 months post-Lapiplasty® Procedure, in comparison to baseline visit.
9. Change in Range of Motion - 1st MTP dorsiflexion and plantarflexion at 12 months and 24 months post-Lapiplasty® Procedure, in comparison to baseline visit.
10. Change, if any, in initial incision length during Lapiplasty® Procedure.
11. Change in radiographic foot length and width at 12 months post-Lapiplasty® Procedure in comparison to baseline visit.
12. Change in swelling at 6 weeks and 4 months post-Lapiplasty® Procedure as compared to 0-2 week visit.
13. Change in scar quality at 4 months, 6 months, and 12 months post-Lapiplasty® Procedure in comparison to baseline visit.
14. Correlation between amount of time external positioner is actively used during Lapiplasty Procedure with necrosis, blistering, bruising and tissue ulceration events.

[figure not shown]

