#### **7.9 Visit 9 – 24 Month Follow-Up ( $\pm$ 2 months)**

The following must be conducted:

- Digital photograph of operative foot, not required
- Radiographic Imaging
- Clinical Exam of Operative Foot, including Clinical Pain Assessment at 1st TMT Joint
- POSAS
- QOL Measurements
- VAS Pain Scale
- Range of Motion
- General Satisfaction Questionnaire (Appendix 10)
- Secondary Surgical Interventions
- Medications Review
- Adverse Event Assessment
- Health Economic Outcomes
- Radiographic Measurements

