### 7.10 Unscheduled Visit

If a subject requires an unscheduled visit due to a complication associated with the Lapiplasty® Procedure or Lapiplasty® device, for suspected non-union or for additional follow-up on start of WB activities, the following should be conducted:

- Reason for Visit (complication/adverse event, suspected non-union or WB instructions)
- Clinical Exam of Operative Foot
- Return to WB Activities, if applicable
- Adverse Event Assessment
- Radiographic Imaging (if required due for assessment of complication)

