### **Visits 6 -9**

- IMA (Intermetatarsal angle)
- HVA (Hallux Valgus Angle)
- Lateral Round Sign Present
- TSP (Tibial Sesamoid Position)
- MAA (Metatarsus Adductus)
- Metatarsal Rotation
- Post-Operative Metatarsal Rotation
- Sesamoid Subluxation
- Sagittal-Plane 1st Metatarsal Position
- Meary's Angle
- AP Talar -1st Metatarsal Angle
- Osseous Foot Width
- 1-2 Metatarsal Length
- MTP (Metatarsal Phalangeal) Osteoarthritis
- Metatarsal-Sesamoid Osteoarthritis
- DMAA
- Sagittal 1st Ray Length
- Lucency at arthrodesis: Yes/No
- Hardware Failure (transverse screw)
  - If Yes, location of screw(s): C1-C2 or C1-M2
- Hardware Failure (screws or plates at 1st TMT Joint)
- Hardware issues, potential complications or adverse events based on radiographic review

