6.4.8 Recurrence

Recurrence (loss of correction) is considered to have occurred at 24-months post-procedure if any two of the following 3 criteria are met: IMA of $\geq 12^\circ$, HVA $\geq 20^\circ$, TSP ≥ 4 . An alternative definition of recurrence will also be applied: HVA $\geq 15^\circ$.

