6.4.9 Non-union

Non-union is defined as pain at the TMT joint plus one or more of the following: lucency, hardware failure, or recurrence.

7 Statistical Analysis

All continuous variables will be summarized using the following descriptive statistics: n, mean, standard deviation, median, minimum, maximum, and where appropriate 95% confidence intervals (CIs). The frequency and percentages of observed levels will be reported for all categorical measures. In general, all summary tables will be annotated with the total population size relevant to that table, including any missing observations. Data listings will be sorted by site, subject, and when appropriate by visit type within subject.

Two-sided T-tests will be generated for change from baseline analyses. P-values ≥ 0.001 will be reported to 3 decimal places; p-values less than 0.001 will be reported as “ <0.001 ”. P-values less than 0.05 will be considered statistically significant. The mean, standard deviation, and any other statistics other than quantiles, will be reported to one decimal place greater than the original data. Quantiles, such as median, or minimum and maximum will use the same number of decimal places as the original data. Estimated parameters, not on the same scale as raw observations (e.g. regression coefficients) will be reported to 3 significant figures.

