7.2.2 Secondary Effectiveness Analysis

Effectiveness analyses will be performed on the following secondary endpoints:

- 1) Percentage of subjects with recurrence at 12 months where recurrence is defined as meeting 2 of the following 3 criteria: IMA of $\geq 12^\circ$, HVA $\geq 20^\circ$ and TSP ≥ 4 .

- 2) Percentage of subjects with recurrence at 12 months and 24 months where recurrence is defined as HVA >15°.
- 3) Percentage of subjects with recurrence at 12 months and 24 months where recurrence is defined as HVA >20°.
- 4) Percentage of subjects with successful correction at 6 weeks.
- 5) Change from baseline in radiographic angular/positional alignment for HVA, IMA, TSP, and sagittal plane at 6 weeks, 4 months, 6 months, 12 months, and 24 months.
- 6) Percentage of subjects with non-union (absence of clinical/radiographic healing) at 12 months.
- 7) Time to weight-bearing in a controlled ankle motion (CAM) boot, in days.
- 8) Time to weight-bearing in shoes, in weeks.
- 9) Time to return to full unrestricted activity, in months.
- 10) Change from baseline in pain at the base of the big toe (bunion related) assessed via VAS at 0-14 days, 14-21 days, 6 weeks, 4 months, 6 months, 12 months, and 24 months.
- 11) Change from baseline in Quality of Life at 6 months, 12 months, and 24 months as measured by PROMIS-29 (for adult subjects), PROMIS-25 (for pediatric subjects), and MOxFQ (for all subjects).
- 12) Change from baseline in range of motion of the 1st MTP dorsiflexion, plantarflexion, and dorsiflexion plus plantarflexion at 4 months, 6 months, 12 months, and 24 months.
- 13) Change from baseline in foot swelling measurements at 0-14 days, 14-21 days, 6 weeks, 4 months, 6 months, and 12 months.
- 14) Summary of POSAS responses over time at 4 months, 6 months, 12 months, and 24 months.

Statistical summaries will be produced in accordance with section 7, and listings will be generated by site, subject, and visit (where applicable) within subject.

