Table 5	Proportion of subjects with non-union at 12 months post-procedure, ITT Population
Table 6	Foot Swelling, ITT Population
Table 7	Time to weight-bearing, to full unrestricted activity, and to return to work, ITT Population
Table 8	Change from baseline in radiographic angular/positional alignment, ITT Population
Table 9	Change from baseline in range of motion (ROM) , ITT Population
Table 10	Change from baseline in pain at the base of the big toe as assessed by VAS, ITT Population
Table 11	Change from baseline in QoL as assessed by MOxFAQ, ITT Population
Table 12	Concomitant procedures, ITT Population
Table 13	Incision Length, ITT Population
Table 14	Metatarsalgia, ITT Population
Table 15	Lengthening, ITT Population
Table 16	Patient Satisfaction Survey, ITT Population
Table 17	Adverse events, ITT Population
Table 18	Serious adverse events, ITT Population
Table 19	Adverse events leading to death, ITT Population
Table 20	Adverse events leading to study discontinuation, ITT Population
Table 21	POSAS, ITT Population
Table 22	Change from Baseline in QoL as Assessed by PROMIS (Adult), ITT Population
Table 23	Change from Baseline in QoL as Assessed by PROMIS (Pediatric), ITT Population
Table 24	Major Protocol Deviations, ITT Population
Table 25	Summary of Clinical Complications
Listing 1	Subject Disposition, ITT Population
Listing 2	Complications, AEs, and HW Failures, ITT Population
Listing 3	All Protocol Deviations, ITT Population
Listing 4	Metatarsalgia, ITT Population

Listing 5	Radiographic Measurements, ITT Population
Listing 6	Concomitant Procedures, ITT Population
Listing 7	Device and Product Experience, ITT Population

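### Non-union is scored only at month 12, with no rule for subjects revised or exited earlier or for cases first evident at month 24, and its radiographic half does not require a sign at the fusion site

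*SAP*

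**What the plan says.** **Timing.** SAP 7.2.2 item 6 analyses "Percentage of subjects with non-union (absence of clinical/radiographic healing) at 12 months". Table 5 in the list of statistical outputs is "Proportion of subjects with non-union at 12 months post-procedure, ITT Population". The protocol's secondary endpoint 2 has the same landmark: "Non-union defined as lucency at TMT joint, hardware failure and/or loss of correction (recurrence), plus clinical pain at first TMT joint at 12 months". No 24-month or cumulative non-union output is listed.

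**Definition.** SAP 6.4.9: "Non-union is defined as pain at the TMT joint plus one or more of the following: lucency, hardware failure, or recurrence". It names no visit and does not say how a revised subject is scored. SAP 6.4.8 defines the recurrence component: "Recurrence (loss of correction) is considered to have occurred at 24-months post-procedure if any two of the following 3 criteria are met", the criteria being cut-offs on IMA, HVA and TSP.

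**Data collected outside the 12-month visit.** Protocol 7.10 provides an unscheduled visit "for suspected non-union or for additional follow-up on start of WB activities". At 24 months, protocol 7.9 requires a foot examination "including Clinical Pain Assessment at" the first TMT joint. Appendix 4 has the central radiologist read lucency and hardware failure at Visits 6 to 9. One hardware item begins "Hardware Failure (transverse screw"; failure of screws or plates at the first TMT joint is a separate item.

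**Missing data and exits.** SAP 6.3 analyses effectiveness on observed data with nothing imputed. Protocol 4.2.5 lists failure of the device or index procedure among the reasons for leaving the study.

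**The concern.** Objective 3 asks whether early weight-bearing affects union rates, and Table 5 holds the only union figure that answers it. A single look at month 12 records the state of the joint on that day, not whether fusion failed. A subject whose non-union was found and revised before month 12 may have recovered by then, or may have left the study. A subject whose non-union shows itself between months 12 and 24 comes too late. In each case the event is absent from the rate.

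The definition raises a second, smaller question in the other direction. Beyond TMT pain, it accepts signs that do not assess the arthrodesis, so some counted cases might not be failures of fusion. With very few events expected, one or two subjects classified differently would visibly change the reported rate.

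**Working it through.** **1. How the rules score each type of case**

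| Case | Rule that applies | Result in Table 5 |
|---|---|---|
| Revised for non-union before month 12, no TMT pain at month 12 | 6.4.9 requires pain | Scored as united |
| Revised before month 12, still has TMT pain and a qualifying sign | 6.4.9 met | Counted |
| Exits before month 12 | 6.3, observed data only | Missing |
| First meets the definition at month 24 | 7.2.2 item 6 uses month 12 only | Not counted |
| Fused joint, TMT pain, HVA and TSP both past the recurrence cut-offs | 6.4.9 met through recurrence | Counted |
| Fused joint, TMT pain, failed transverse screw | 6.4.9 does not say which hardware | Counted if any hardware qualifies |
| Recurrence with pain only at the bunion | 6.4.9 requires TMT pain | Not counted |

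The recurrence component also has a date problem. SAP 6.4.8 places recurrence at 24 months, while item 6 is a 12-month endpoint. Item 1 of 7.2.2 applies the same two-of-three rule at 12 months, but 6.4.9 does not say which applies.

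**2. Reproducing the only non-union figure in the documents**

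Protocol section 1.0 and the SAP introduction cite 1.6% symptomatic non-union in a retrospective study of 72 patients, with 61 feet at one year.

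- 1/61 = 1.64%, which rounds to 1.6%; 1/72 = 1.39% does not match, so the denominator is the 61 feet.
- Check: 59/61 = 96.7%, the other rate cited from that study.
- The exact (Clopper-Pearson) 95% CI for 1/61 is 0.04% to 8.8%.

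**3. What one subject is worth**

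- Planned size is 200 subjects (protocol 9.2), with no formal calculation.
- Expected non-unions at the cited rate: 200 × 1/61 = 3.3. Probability of at least one: 1 − (60/61)^200 = 96%.
- One subject moves the rate by 1/200 = 0.5 points. Against 3/200 = 1.5%, that is 0.5/1.5, or one third.

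**4. Illustration**

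Assume 3 true non-unions in 200 (1.5%, exact 95% CI 0.31% to 4.32%) and all 200 seen at month 12. The splits below are assumptions; the documents give none.

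| Revised early, pain-free at month 12 | First evident after month 12 | Fused joint but counted | Table 5 count | Rate |
|---|---|---|---|---|
| 0 | 0 | 0 | 3 | 1.5% |
| 1 | 0 | 0 | 2 | 1.0% |
| 2 | 0 | 0 | 1 | 0.5% |
| 1 | 1 | 0 | 1 | 0.5% |
| 0 | 0 | 1 | 4 | 2.0% |
| 0 | 0 | 3 | 6 | 3.0% |
| 1 | 1 | 2 | 3 | 1.5% |

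If the early case in the second row exits instead of healing, the rate is 2/199 = 1.01%, practically the same. The last row shows that errors in both directions can cancel and leave no trace in the rate.

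**The case against.** **The events are reported elsewhere.** A reader might infer that a non-union revised at month 7 disappears from the study. The documents do not support that. Protocol 7.12 records secondary surgical interventions with reason and action taken. SAP 7.3.1 covers related adverse events to the last visit, SAP 7.3.2 covers complications through 24 months, and Table 25 and Listing 2 are planned. This objection stands against any claim that the cases are lost. It does not supply the missing rate. Although protocol 8.1.8 plans MedDRA coding, SAP 7.3 says its analysis will not use coding dictionaries, and adverse events are summarised by reported term. SAP 7.3.2 has no non-union category. The summary of events leading to device removal or surgery promised in 7.3.1 has no table of its own in the output list.

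**TMT pain is always required.** A reader might infer that painful recurrence anywhere in the foot is scored as non-union. It is not: pain must be at the first TMT joint, which protocol 7.12 assesses by stress and palpation. A false positive needs TMT pain, a fused joint, and either recurrence or a hardware failure away from that joint. The documents do not say how often that happens.

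**Early revisions need not be scored as united.** It is tempting to say that the worst cases are the ones most likely to be scored as healed. The documents give no basis for that. A revised subject may still have pain and a qualifying sign, or may be missing.

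**Loss of correction has its own outputs.** SAP 7.2.2 items 1 to 3 and Table 3 report recurrence at 12 and 24 months, so the composite does not remove that half of objective 3.

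**The landmark is the protocol's own, and the study is descriptive.** The SAP follows the protocol here, and no threshold hangs on this rate. That is a reason to keep the 12-month figure and add to it rather than replace it. The interval for 3/200 also contains every shifted rate in the illustration, so the shifts lie within sampling error. They are nonetheless systematic for a given type of case, and the rate could be reported without them.

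**Conclusion.** The point holds as a gap in one secondary endpoint. Table 5 omits non-unions that were revised and pain-free before month 12, loses those that exit, and ignores those first evident at month 24. These omissions lower the rate. The loose radiographic half can raise it. The net direction and the number of subjects affected cannot be derived from the documents.

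The size is known only per subject: 0.5 points each at 200 subjects, about a third of a 1.5% rate. That comparison rests on a cited rate built on one event in 61 feet, with an interval up to 8.8%, and the documents do not give that study's definition of non-union. The primary endpoint is unaffected. The change is still worth making, because this is the only union rate serving objective 3 and most of what is needed is already collected.

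**What to change.** In SAP 6.4.9, 7.2.2 item 6 and Table 5:

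1. Count any subject with a recorded revision or supplemental fixation for non-union before month 12 as a non-union in the 12-month rate, including a subject who then exits.
2. Add a row for cumulative non-union through 24 months: definition met at the 12- or 24-month visit, or revision for non-union at any time.
3. State that recurrence within this definition is assessed at the same visit as the TMT pain.
4. Show cases that qualify by lucency or by hardware failure at the first TMT joint separately from those that qualify only by recurrence or a transverse screw.
5. Keep the protocol's present 12-month figure beside these rows, and print the number with no 12-month assessment.

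The cost is SAP wording and a few rows in Table 5. The inputs are already on the forms: the reason for each intervention, TMT pain at 12 and 24 months, lucency, and the two separate hardware items. The downside is that the reported rate may come out slightly higher. Subjects who exit early without a recorded revision stay missing, which is why that number should be shown.

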## **Foot Measurements–**

### **Baseline and Pre-operatively**

Using a flexible tape measure, measure the circumference of the forefoot using the most prominent projection at the medial 1st metatarsal head and the lateral 5th metatarsal head as the starting reference points. Measure in a circumferential manner. Remove slack from the tape so that it lays flat on the skin.

Using a flexible tape measure, measure the circumference of the foot using the 1st TMT articulation as the starting reference point. Determine the position of the TMT via manipulation of the metatarsal through a dorsiflexion/plantarflexion movement. Palpation and visualization of the joint puckering through the soft tissue will allow for the approximation of this landmark. Mark the area with a surgical marking pen for reference. If this is unsuccessful in allowing the surgeon to determine the level, a metallic bb marker can be placed on the skin and plain film radiographic imaging can be utilized to approximate the anatomy. Determine the TMT position and measure in a circumferential manner. Remove slack from the tape so that it lays flat on the skin.

Using a flexible tape measure, measure the circumference of the ankle using the medial and lateral malleolus as reference points. Hold the measuring tape just superior to the inferior edge of the medial malleolus. Wrap the tape around the ankle, remove all slack and ensure the tape is flat on the lateral malleolus. The measurement should be made perpendicular to the longitudinal axis of the tibia and fibula.

Measure the circumference of the mid-calf at the tibia. Approximate the Myotendinous junction of the gastroc. Measure the distance from this landmark to the popliteal fossa. Determine the midline and measure in a circumferential manner. Remove slack from the tape so that it lays flat on the skin.

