### **Post-operatively**

Using a flexible tape measure, measure the circumference of the forefoot using the most prominent projection at the medial 1st metatarsal head and the lateral 5th metatarsal head as the starting reference points. Measure in a circumferential manner. Remove slack from the tape so that it lays flat on the skin.

Using a flexible tape measure, measure the circumference of the foot using the midpoint of the surgical incision as the starting reference point. Determine the midline and measure in a circumferential manner. Remove slack from the tape so that it lays flat on the skin.

Using a flexible tape measure, measure the circumference of the ankle using the medial and lateral malleolus as reference points. Hold the measuring tape just superior to the inferior edge of the medial malleolus. Wrap the tape around the ankle, remove all slack and ensure the tape is flat on the lateral malleolus. The measurement should be made perpendicular to the longitudinal axis of the tibia and fibula.

Measure the circumference of the mid-calf at the tibia. Approximate the Myotendinous junction of the gastroc. Measure the distance from this landmark to the popliteal fossa. Determine the midline and measure in a circumferential manner. Remove slack from the tape so that it lays flat on the skin.

**Range of Motion** – Dorsiflexion and plantarflexion should be measured while subject is passive and non-weightbearing with the study provided goniometer. To measure ROM, the arms of goniometer should be lined up parallel to longitudinal axis of the 1st metatarsal and proximal phalanx of the hallux with the axis at the center of rotation of the first metatarsal head.

**Radiographic Measurements** - Radiographic measurements will be analyzed by a third-party independent radiologist and entered into Clinindex. The radiographic measurements that will be collected, at a minimum, are provided in **Appendix 4**. Additional exploratory radiographic measurements may be collected without requiring a protocol amendment.

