1.2.2 Secondary Endpoints

- 1) Change from baseline in radiographic angular/positional alignment at 6 weeks, 4 months, 6 months, 12 months, and 24 months post-Lapiplasty® Procedure.
- 2) Percentage of subjects with absence of clinical/radiographic healing, or non-union, at 12 months post-Lapiplasty® Procedure.
- 3) Clinical complications through 24-month follow-up visit due to the Lapiplasty® System Implants, the Lapiplasty® Procedure, the post-operative weight-bearing protocol or health conditions that could affect other outcome measures.
- 4) Time to start weight-bearing in boot, in days.
- 5) Time to start weight-bearing in shoes, in days.
- 6) Time to return to full unrestricted activity, in days.
- 7) Change from baseline in pain at the base of the big toe (bunion related) assessed via a Visual Analog Scale (VAS) at 0-14 days, 14-21 days, 6 weeks, 4 months, 6 months, 12 months, and 24 months.
- 8) Change from baseline in Quality of Life at 6 months, 12 months, and 24 months as measured by PROMIS-29 (for adult subjects), PROMIS-25 (for pediatric subjects), and MOxFAQ (for all subjects).
- 9) Change from baseline in range of motion (ROM) of 1st MTP dorsiflexion and plantarflexion at 12 months and 24 months.
- 10) Change, if any, in incision length during the Lapiplasty® Procedure.
- 11) Change from baseline in radiographic foot length and width at 12 months post-Lapiplasty® Procedure.
- 12) Change in swelling at 6 weeks and 4 months post-Lapiplasty® Procedure as compared to 0-14 day visit.
- 13) Change in scar quality at 4 months, 6 months, and 12 months post-Lapiplasty® Procedure.
- 14) Correlation between amount of time external positioner is actively used during Lapiplasty® Procedure with necrosis, blistering, bruising, and tissue ulceration events.

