6.1 Baseline

Baseline values are those which were collected at the Baseline visit (Visit 1). If a baseline value is missing, then the most recent value collected within 90 days prior to the Index Procedure will be used.

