6.4.2 Change from Baseline

Change from baseline will be determined for ROM, VAS, PROMIS, MOxFAQ, and radiographic measurements (IMA, HVA, tibial sesamoid position (TSP), sagittal plane). It will be calculated as value at timepoint of interest minus value at baseline.

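### SAP 7.2.2(13) analyses swelling as change from pre-operative baseline, so the declared contrast with the 0-14 day visit is never analysed

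*SAP*

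**What the plan says.** **Endpoint.** Protocol section 3.0, secondary endpoint 12, reads "Change in swelling at 6 weeks and 4 months post-Lapiplasty® Procedure as compared to 0-2 week visit". The protocol synopsis names the same visit by its 0-14 day label. SAP 1.2.2 item 12 agrees with the synopsis: "Change in swelling at 6 weeks and 4 months post-Lapiplasty® Procedure as compared to 0-14 day visit".

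**Analysis.** SAP 7.2.2 item 13 reads "Change from baseline in foot swelling measurements at 0-14 days, 14-21 days, 6 weeks, 4 months, 6 months, and 12 months". SAP 6.1 defines baseline as Visit 1, before surgery. SAP section 7 attaches two-sided t-tests to change-from-baseline analyses and calls p below 0.05 significant. SAP 6.4.2 lists the variables that get a change from baseline ("Change from baseline will be determined for ROM, VAS, PROMIS, MOxFAQ, and radiographic measurements"), and swelling is not among them. The title of SAP Table 6 says only that it shows foot swelling and names no contrast.

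**Measurement.** Protocol 7.12, Foot Measurements, describes four girths: forefoot, mid-foot, ankle and mid-calf. For the mid-foot, the instruction at baseline and pre-operatively is to "measure the circumference of the foot using the 1st TMT articulation as the starting reference point". After surgery it is to "measure the circumference of the foot using the midpoint of the surgical incision as the starting reference point". The forefoot instruction is the same before and after: "measure the circumference of the forefoot using the most prominent projection at the medial" 1st metatarsal head, and round the 5th. The ankle and calf instructions do not change either. Foot measurements are scheduled at Visits 1 to 8 in both documents.

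**The concern.** The visit that the endpoint uses as its reference appears in item 13 as one of six outcome visits. No item in SAP section 7 compares 6 weeks or 4 months with it. Protocol 9.8 asks the SAP to give a rationale for changes to the analysis, and none is given here.

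The substituted contrast is also the harder one to interpret. Change from baseline spans the operation, so for two girths it can include something other than oedema:

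- **Mid-foot:** the tape starts from a differently defined point before and after surgery.
- **Forefoot:** the tape runs over the bunion. Protocol Appendix 5 lists removal of the bump as a potential benefit, Protocol 7.12 allows medial eminence resection as a concomitant procedure, and secondary endpoint 11 measures change in foot width. The protocol therefore expects the bony contour here to change.

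At stake is one secondary endpoint. As written, a reported significant change from baseline in these two girths could not be attributed to swelling alone, and the declared contrast would be missing from the report.

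**Working it through.** The documents state no figure for swelling and no sample size calculation, so there is nothing to reproduce. The check is a comparison of texts, followed by an illustration on assumed values.

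**1. Reference visit and times**

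| Place | Reference | Times analysed |
|---|---|---|
| Protocol synopsis, endpoint 12 | 0-14 day visit | 6 weeks, 4 months |
| Protocol 3.0, endpoint 12 | 0-2 week visit | 6 weeks, 4 months |
| SAP 1.2.2 item 12 | 0-14 day visit | 6 weeks, 4 months |
| SAP 7.2.2 item 13 | Baseline (Visit 1) | Visits 3 to 8, that is 0-14 days to 12 months |

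The first three name the same visit and times. The fourth differs from all of them in its reference.

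**2. What each contrast estimates.** Write a girth as a bony-and-landmark part plus swelling. Let s_v be swelling at post-operative visit v relative to the pre-operative foot. Let b be the post-operative minus the pre-operative bony-and-landmark part. Then:

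- change from baseline at visit v = s_v + b
- change from Visit 3 at visit v = (s_v + b) − (s_3 + b) = s_v − s_3

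For ankle and calf the landmark instructions are unchanged and nothing suggests b differs from zero. For forefoot and mid-foot, b need not be zero. It drops out of the second contrast as far as landmark and bone position are the same at both post-operative visits.

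**3. Illustration (assumed values).** Take s_3 = 2.0 cm and s at 6 weeks = 0.5 cm.

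| b (cm) | Change from baseline, 0-14 days | Change from baseline, 6 weeks | Change from Visit 3, 6 weeks |
|---|---|---|---|
| 0 | 2.0 | 0.5 | −1.5 |
| −0.3 | 1.7 | 0.2 | −1.5 |
| −0.5 | 1.5 | 0.0 | −1.5 |
| −1.0 | 1.0 | −0.5 | −1.5 |

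The same residual swelling reads as present, absent or negative against baseline, depending on b.

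**4. How small a b the t-test would flag.** The documents give no SD, so assume an SD of change of 0.5 to 1.5 cm. By the normal approximation, an observed mean shift reaches two-sided p<0.05 at 1.96 × SD / √n.

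- n = 200 (the planned maximum): 1.96 × 0.5 / 14.14 = 0.07 cm, and 1.96 × 1.5 / 14.14 = 0.21 cm.
- n = 150: 1.96 × 0.5 / 12.25 = 0.08 cm, and 1.96 × 1.5 / 12.25 = 0.24 cm.

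With SD 1.0 cm, n = 200 and no true swelling, the standard error is 0.0707 cm. A true b of 0.2 cm would be declared significant with probability Φ(0.2/0.0707 − 1.96) = Φ(0.87), about 81%. For b = 0.3 cm it is about 99%.

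**5. Can the endpoint be recovered from item 13?** The point estimate can, as the difference of two reported mean changes, if the same subjects have both visits. Its variance is Var(change at v) + Var(change at Visit 3) − 2 × their covariance. The covariance is not reported, so the SD, confidence interval and p-value cannot be recovered.

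**The case against.** A reader might infer that the SAP counts bunion removal as reduced swelling, that two girths are unusable against baseline, and that the 0-14 day reference is free of problems. The documents do not support any of these in full.

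- **Mid-foot.** Protocol 5.2.1 describes a dorsal incision of about 3.5 cm through which the 1st TMT joint is released, and incisions above 4.0 cm are excluded. If the joint lies within the incision, its midpoint is at most about 2 cm away. It may simply stand in for a joint that can no longer be found by moving it once fused. The landmark wording does change, but the resulting girth error may be small.
- **Forefoot.** That correction lowers this girth is a fair inference. How much is not stated. Centimetre figures can be produced only by assuming a forefoot shape and an amount of narrowing, neither of which is in the documents. Protocol Appendix 4 has osseous foot width read at Visit 1 and Visits 6 to 9, so the bony change can be described from 4 months on, though not at 6 weeks.
- **The 0-14 day reference.** Visit 3 can fall on any day from 0 to 14, when swelling may be changing quickly. Protocol 5.3 lets compression socks start at Visit 3 or 4 and continue to about 4 months. These sources of variation do not cancel, and a fall from an early post-operative value is close to certain.
- **Use of baseline.** Whether the foot has returned to its pre-operative girth is a useful question. Barring that display would be a preference, not a correction.
- **Whether a test is planned.** SAP 6.4.2 omits swelling and Table 6 does not mention baseline, unlike Tables 8 to 11, 22 and 23. A t-test follows from item 13 read with SAP section 7, but the SAP is not consistent on this.
- **Weight.** This is one of 14 secondary endpoints in a study described as mainly descriptive.

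All of this limits the size of the point. None of it reconciles the two reference visits.

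**Conclusion.** The contradiction in the reference visit is plain on the text and needs no assumption. The declared contrast has no planned analysis, although the data for it are collected.

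The interpretive problem with change from baseline is real in kind for mid-foot and forefoot, and absent from the ankle and calf instructions. Its size is not established. The thresholds of 0.07 to 0.21 cm show only how sensitive a test on 200 subjects would be under an assumed SD; they are not estimates of the artefact. The post-operative contrast is better protected against landmark and bony change, but not against visit timing or compression. No primary or safety conclusion depends on this point. It should be corrected before the SAP is applied.

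**What to change.** 1. In SAP 7.2.2 item 13 and Table 6, make the within-subject change from Visit 3 (0-14 day) at 6 weeks and 4 months the endpoint analysis, for each of the four girths separately, with n, mean, SD and 95% CI.
2. Keep change from baseline as a summary labelled supplementary, with a note that forefoot and mid-foot changes can include bony realignment and the change of landmark.
3. Bring SAP 6.4.2 into line, so that it is clear which swelling contrasts are calculated and whether either is tested.
4. Use one name for the reference visit in Protocol 3.0, the synopsis and the SAP.

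Cost: wording changes and one extra contrast in an existing table. Girths are already taken at Visits 1 to 8, so no new data are needed.
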